9.2. Not / permitted medications during the study

Administration of penicillin-based antibiotics will not be permitted during the study period as this may interfere with the results of assays. The use of probenecid, NSAIDs, or other medications which may significantly alter the Bicillin® L-A PK will also not be permitted during the study period. Participants will be asked to avoid all prescription and over-the-counter medications and supplements for at least seven days prior to commencement and during the study. Probenecid and NSAIDs other than paracetamol and ibuprofen should be avoided for 14 days prior and during the study. The following rescue medication will be permitted:

- (a) Loratadine, 10mg, non-sedating antihistamine, for the treatment of itch.
- (b) Prednisolone, 1mg/kg, steroid, for treatment of rash.
- (c) Adrenaline 0.3mg/0.3ml auto-injector IM will be available at time of administration in the event of anaphylactic reaction.

10. Study Treatment

10.1. Randomisation and blinding

- (a) Randomisation of participants to first injection of either SC or IM injection will occur post-enrolment. Randomisation will be by means of a random number generator.
- (b) Blinding will occur in a single blinded fashion as it is not possible to blind the clinician who will administer the injection. Both injections will utilise the outer upper quadrant of the gluteal area and participants will be blinded to whether injection is SC or IM.

10.2. Methods to reduce bias

Bias - results will not be processed until after all data collection is complete. The potential sources include the participant perception of pain associated with injection, and previous experience. The same clinician will perform all injections and will be instructed to follow the same procedure for each injection to minimise bias.

10.3. Maintenance of any blinding records or randomisation codes and procedures for breaking codes

Maintenance of randomisation codes will be in accordance with GCP; if a subject is admitted to hospital for management from a complication of the administration of trial product, the study coordinator will break blinding to allow for medical care to proceed unhindered.

10.4. IMP dosing, registration, formulation, packaging, labelling, and storage

10.4.1. Registration

Benzathine Penicillin G is marketed in Australia under the market name of Bicillin® L-A, and is registered by the TGA. Other forms of the drug exist as a combination medication but are not marketed in Australia. Bicillin® L-A comprises a single active compound: BPG. Attached is the product information sheet from Pfizer Australia in Appendix 1, which contains further information regarding the susceptible bacteria, storage, administration dosage, and over-dosage information.

There is no comparator product in this trial.

10.4.2. Formulation

BPG is comprised of a suspension of two benzylpenicillin molecules and a benzathine molecule forming a white crystalline powder that is very slightly soluble in water and sparingly soluble in alcohol. It is approved for deep IM injection. Bicillin® L-A refers to the resultant aqueous suspension which also contains a citrate buffer and, as weight/volume, approximately 0.5% lecithin, 0.6% carboxymethylcellulose, 0.6% povidone, 0.1% methylparaben, and 0.01% propylparaben. Bicillin® L-A is an opaque, viscous suspension. In Australia, it is available in 2.3ml corresponding to 1,200,000 units of penicillin G. Administration of Bicillin® L-A 1,200,000 units via deep IM injection results in prolonged serum concentrations of the active metabolite; penicillin G levels of 2.25ng/mL may still be detectable for four weeks.

See PIS for additional information.

10.4.3. Packaging, labelling and storage

The IMP (Bicillin® L-A) will be labelled in accordance with annex 13 of the “guide to good manufacturing practice for medicinal products annexes”.⁸¹ The IMP is registered by the therapeutic good administration of Australia. The IMP will be refrigerated at 2-8°C, and will not be frozen. The product information sheet from Pfizer Australia is attached (see Appendix 1), and contains further information regarding the susceptible bacteria, storage, administration dosage, and over-dosage information.

10.5. Accountability of IMP

The investigator is responsible for maintaining adequate records of the disposition of the received IMP, including date, quantity and serial/batch numbers, records of who received the IMP, and records of any IMP destroyed/discarded (intentionally/unintentionally). All records will be available for inspection by the monitor or sponsor if required.

10.6. Preparation, administration and dose

Bicillin® L-A will be prepared in accordance with the manufacturer's guidelines.

Intramuscular injection

1. On morning of injection, the Bicillin® L-A 1016.6mg or 1.2MIU (2.3ml) and supplied needle will be removed from the fridge at least 3 hours prior to injection time to allow suspension to reach room temperature. The syringe will later be further warmed by rolling the syringe between palms prior to injection.
2. The syringe will be placed in a clean field.
3. The participant will have consent checked and will be placed in prone position. Participants will nominate a buttock for the first administration period and asked to expose the buttock area. In second administration period, the opposite buttock will be used.
4. The injection will be undertaken in a clinical suite screened for privacy, with access to medical resuscitation equipment; adrenaline will be available. The injection will be performed by a suitably qualified investigator who has undertaken the online training module on BPG injection developed by Pfizer with RHDAustralia (<https://www.rhdaustralia.org.au/administering-bicillin>).
5. A screen will be set up to prevent participant observation of the US monitor and injection site. Landmarks will be palpated to estimate the dorso-gluteal injection site.
6. US will be used to confirm the injection site and determine the thickness of SC tissue. Distance from skin to at least 5mm into gluteal muscle will be measured.
7. Skin will be cleaned and prepped using alcohol swab.
8. Using sterile technique, the needle will be attached to the syringe.
9. Manual pressure will be applied over the site for 30 seconds prior to injection.
10. Formation of 'Z' tract. The needle will be inserted rapidly at an angle of 90° to skin surface with no pressure on the plunger. Confirmation of needle tip location in IM tissue with US and a safe distance from vasculature and nerves. Aspiration to prevent complication of IV injection: if aspiration of blood is noted, the needle will be withdrawn and removed, and the blood expelled from the chamber. The needle will be discarded, and a new needle attached. Step 6 will be repeated.
11. The Bicillin® L-A will be injected slowly in 8-10 small aliquots over 3 minutes, monitored with a timer.
12. The needle will be removed, and light pressure applied directly over the injection site with gauze.
13. The time of completion of the injection will be documented, and sampling using DBS and NRS post-injection carried out as scheduled using the end of injection time as the reference point.
14. The participant will be monitored for AEs in the clinical trial facility for 12 hours post-injection.
15. Participant pain scores will be recorded at the time intervals specified above.

16. The participant will be discharged and instructed to follow up at the appropriate times.

Subcutaneous injection

1. On morning of injection, the Bicillin® L-A 1016.6mg or 1.2MIU (2.3ml) and supplied needle will be removed from fridge at least 3 hours prior to injection time to allow suspension to reach room temperature. The syringe will later be further warmed by rolling the syringe between palms prior to injection.
2. The syringe will be placed in a clean field.
3. The participant will have consent checked and placed in prone position. Participants will nominate a buttock for the first administration period and asked to expose the buttock area. In second administration period, the opposite buttock will be used.
4. The injection will be undertaken in the clinical suite screened for privacy, with access to medical resuscitation equipment; adrenaline will be available. The injection will be performed by a suitably qualified investigator who has undertaken the online training module on BPG injection developed by Pfizer with RHD Australia (<https://www.rhdaustralia.org.au/administering-bicillin>).
5. A screen will be set up to prevent participant observation of the US monitor and injection site. Landmarks will be palpated to estimate the dorso-gluteal injection site.
6. US will be used to confirm the injection site and determine the thickness of SC tissue. Distance from skin to the gluteal muscle will be measured.
7. Skin will be cleaned and prepped using alcohol swab.
8. Using sterile technique, the needle will be attached to the syringe.
9. Manual pressure will be applied over the site for 30 seconds prior to injection.
10. The needle will be inserted rapidly at an angle of 45° to skin surface with no pressure on the plunger. Confirmation of needle tip location in SC tissues with US and safe distance from vasculature and nerves. Aspiration to prevent complication of inadvertent IV injection: if aspiration of blood is noted, the needle will be withdrawn and removed, and the blood expelled from the chamber. The needle will be discarded, and a new needle attached. Step 6 will be repeated.
11. The Bicillin® L-A will be injected slowly 3 minutes monitored with timer.
12. The needle will be removed, and light pressure applied directly over the injection site with gauze.
13. The time of completion of the injection will be documented, and sampling using DBS and NRS post-injection carried out as scheduled using the end of injection time as the reference point.
14. The participant will be monitored for AEs in the clinical trial facility for 12 hours post-injection.
15. Participant pain scores will be recorded at the time intervals specified above.
16. The participant will be discharged and instructed to follow up at the appropriate times.

10.7. **Treatment adherence**

The IMP will be administered by a study investigator; no IMP will be required to be taken outside of the direct supervision of a study investigator.

11. Assessment of Safety

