9.1.9. Sampling schedule

It is expected the study will occur over an 18-week period. There will be a maximum of 26 DBS samples taken from each participant through the study period. Additionally, baseline blood tests will be performed in the screening period. A serum sample will be taken at 12 hours and at 14 days post-injection to compare penicillin levels to DBS. Participants will be recruited in month 1; after consent and screening tests, they will then be randomised to receive IM or SC Bicillin® L-A in month 1 as per the schedule (a-e):

(a) Enrolment and screening (2 weeks).

Potential participants will be screened according to the clinical criteria as described in section 6.5. They will then undergo the consent process, the required screening including history, and examination and screening blood tests as outlined in section 9.1.4-9.1.5. If any significant abnormalities are found on screening, they will be referred as clinically appropriate for further testing via their general practitioner and exit the study. Those who fulfil all inclusion and no exclusion criteria will then be blinded and randomised to Group A or Group B (see Table 3).

(b) Administration period 1 (6 weeks).

Participants will be randomised to either the SC or IM administration of Bicillin® L-A in the upper outer quadrant of buttock at day zero. The IMP (Bicillin® L-A) will be prepared as per the manufacturer's instruction in the product information sheet. Injection will occur with a 20G needle of appropriate length. The route of administration will be confirmed via real-time ultrasound imaging; the procedure is outlined in section 10.6. DBS samples will be taken at: baseline, then t=2,

6, 12, and 24 hours, followed by day 2, 3, 5, 7, 14, 21, 28, and 42. There is some flexibility in sampling times as demonstrated in Table 4 below. Pain scoring will be taken routinely at: baseline, t=2, 6, 12, 24, 48, and 72 hours, then at day 5, 7, 14, 21, 28, and 42 if injection-associated pain is recorded at the prior visit. Venesection will be conducted at baseline, 12 hours after the dose of BPG and at day 14 for baseline biochemical and haematological profile and to demonstrate concordance between plasma and DBS penicillin concentrations.

(c) Washout period (4 weeks).

Participants will undergo a washout period of at least 28 days after administration period 1.

(d) Administration period 2 (6 weeks).

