After the washout period, participants will receive alternate administration of IM or SC Bicillin® L-A, dependent on the route of administration in period 1. The IMP (Bicillin® L-A) will be prepared as per the manufacturer’s instruction in the product information sheet. Injection will occur with the 20G needle supplied as part of the Bicillin® L-A product. The route of administration will be confirmed via real-time ultrasound imaging. The procedure is outlined in section 10.6. DBS samples will be taken at: baseline, t=2, 6, 12, and 24 hours, followed by day 2, 3, 5, 7, 14, 21, 28, and 42. There is some flexibility in sampling times as demonstrated in Table 4 below. Pain scoring will be taken routinely at: baseline, t=2, 6, 12, 24, 48, and 72 hours, then at day 5, 7, 14, 21, 28, and 42 if injection-associated pain is recorded at the prior visit. Venesection will be conducted on days 0 and 14 to verify the DBS levels.

(e) Post-sampling telephone follow-up (2 weeks).

Participants will be followed up after a 14-day period by telephone to confirm no persisting AEs; if present, they will be formally reviewed by a study team member.

Table 4: Sampling schedule for both administration periods 1 & 2

T: hrs (days)	0	2	6	12	24 (1)	48 (2)	72 (3)	120 (5)	168 (7)	336 (14)	504 (21)	672 (28)	1008 (42)
DBS	Y	Y	Y	Y	Y	Y	Y	Y	Y	Y	Y	Y	Y
Sampling window [‡]	-	±5 min	±15 mins	±30 mins	±4 hours	±8 hours	±12 hours	±1 day	±1 day	±2 days	±2 days	±2 days	±2 days
Pain score	Y	Y	Y	Y	Y	Y	Y	Y*	Y*	Y*	Y*	Y*	Y*
Venesection	-	-	-	Y	-	-	-	-	-	Y	-	-	-
USS	Y	-	-	-	-	-	-	-	-	-	-	Y	-

DBS = dried blood spot; Y = yes; * = possible measurement; USS = ultrasound scan of injection site (see appendix 8)
; [‡] = time in minutes/hours/days following Bicillin® L-A injection.

A study sampling schedule from screening through to follow up phone call is included as Appendix 7 for ease of reference.

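### Section 10.6 specifies aliquots for the intramuscular injection but not for the subcutaneous one, so delivery pattern may be tied to route in the Ka comparison

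*Protocol*

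**What the plan says.** Section 10.6 gives two parallel 16-step lists. Step 11 for the intramuscular route says the product "will be injected slowly in 8-10 small aliquots over 3 minutes, monitored with a timer". Step 11 for the subcutaneous route says it "will be injected slowly 3 minutes monitored with timer".

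Section 10.2, on reducing bias, says that one clinician gives all injections and "will be instructed to follow the same procedure for each injection to minimise bias". Section 10.1 adds that participants are blinded to route and that the injector cannot be.

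The needle is described in three places. Section 9.1.9(b), period 1: "Injection will occur with a 20G needle of appropriate length". Section 9.1.9(d), period 2: "Injection will occur with the 20G needle supplied as part of the Bicillin® L-A product". In section 10.6, step 1 of both lists refers to the needle supplied with the product; the intramuscular list has "supplied needle will be removed from the fridge at least 3 hours prior to injection time".

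**The concern.** The primary endpoint is the absorption rate. Section 6.2 attributes the long profile of the product to slow release from the depot formed at injection, so how that depot is laid down could plausibly affect Ka. The hypothesis in section 7.2 credits any reduction in Ka to the subcutaneous route, and section 5.3 intends the result to guide whether the drug is given at an intramuscular or a subcutaneous site.

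That attribution requires the two injections to differ only in what the route itself entails. Depth, angle and track belong to the route. Dividing the dose into aliquots does not obviously belong to it, yet it is specified for one route only. The injector knows the route every time, so an unspecified step is also settled by someone who is not blinded.

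**Working it through.** **1. The two lists side by side (section 10.6).** Dose, volume (2.3 mL), warming, position, screen, 30 seconds of pressure, aspiration check, ultrasound confirmation, the 3-minute figure and the timer all match. The substantive differences are:

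- Step 6: the depth measured (into the muscle, or to it). Inherent to route.
- Step 10: Z-track at 90°, or 45°, and the tissue in which the tip is confirmed. Inherent to route.
- Step 11: 8-10 aliquots, or no statement. Not evidently inherent to route.

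**2. The plan's own figure.** Section 12.2 gives the pain power for 2 points, SD 1.7 and correlation 0.3. SD of the paired difference = 1.7 × √(2 × (1 − 0.3)) = 2.011. A two-sided paired t-test at 5% (noncentral t) gives 94.7%, 87.9% and 79.9% for n = 15, 12 and 10, against 94.6%, 87.9% and 79.8% stated. The figures reproduce, and this point does not change them. The Ka power cannot be reproduced because the model parameters are not in the protocol.

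**3. What the crossover can separate.** Let τ be the route effect (SC minus IM), γ the delivery-pattern effect in the same direction, and π a period effect (period 2 minus period 1). The expected within-person SC − IM difference is:

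- Group A (IM then SC): τ + γ + π
- Group B (SC then IM): τ + γ − π
- Simple mean over 15: τ + γ + π(nA − nB)/15
- Period-adjusted: τ + γ

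γ always appears added to τ. Period adjustment, sequence terms or a route covariate in the population model cannot split them, because pattern and route never vary separately.

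**4. Sensitivity for Ka (assumed effects, both directions).** If the intramuscular pattern multiplies intramuscular Ka by f, the observed SC:IM ratio is the true ratio divided by f.

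- f = 1.1 to 1.3: with no route effect, 1/f = 0.909 to 0.769, an apparent reduction of 9.1% to 23.1%. A true 40% reduction reads 1 − 0.6/f = 45.5% to 53.8%.
- f = 1/1.1 to 1/1.3: with no route effect, an apparent increase of 10% to 30%. A true 40% reduction reads 1 − 0.6 × 1.1 = 34% down to 1 − 0.6 × 1.3 = 22%.

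Section 12.2 sizes the trial on a 40% reduction and also considers 30%.

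**5. Sensitivity for pain (assumed effects).** With no route effect and n = 15, a pattern effect of 0.25, 0.5 or 1.0 NRS points, in either direction, makes the paired test reject 7.3%, 14.6% or 43.4% of the time instead of 5%.

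**6. The needle.** The section 9.1.9 wording differs by period, so any effect of it belongs in π. In an unadjusted mean it contributes (8 − 7)/15 = 6.7% of its size at an 8/7 split and (11 − 4)/15 = 46.7% at 11/4. With period in the model it contributes nothing. In 20,000 simulated trials at 8/7, with period effects of 0, 1 and 2 points, the period-adjusted type I error was 4.9-5.2%.

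**The case against.** The strongest reply is that subcutaneous step 11 is an incomplete sentence in a near copy of the other list, so a drafting omission is at least as likely as an intended difference in technique. That is fair. A reader might infer that the subcutaneous dose is given as one continuous injection, but the text does not say so. What remains is that the subcutaneous pattern is unspecified: followed literally, technique goes with route; filled in by judgement, it is left to an unblinded injector.

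Second, section 10.2 cannot mean identical steps, since angle and track differ by design, and it may mean only consistency within each route. This weakens the charge of contradiction. It does not supply the missing subcutaneous instruction.

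Third, the pain limb is weak. No score is expressly scheduled during delivery: section 9.1.9 lists baseline and then 2 hours, and Appendix 7 marks 0 h. The subcutaneous pain study cited in section 6.11 found no effect of flow rate (p = 0.79). It did not test aliquots, so it does not settle the matter, but pain should be mentioned only as a possibility.

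Fourth, delivery pattern might legitimately be regarded as part of the route as administered. That position is open to the sponsor, provided the protocol says so.

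**Conclusion.** The discrepancy in step 11 is real. If it is carried out as written, route and delivery pattern are inseparable for Ka and possibly for pain. The confounding is potential, not established. Any pattern effect would enter the contrast at 100% of its size; the figures in steps 4 and 5 of the working rest on assumed effects and show only what such an effect would do.

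Two stronger readings are not supported:

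- *That the size is known and favours the hypothesis.* A reader might treat the aliquots as 8-10 separate spherical depots with release proportional to surface area, giving 8^(1/3) = 2.00 to 10^(1/3) = 2.15 times the surface of one bolus and an SC:IM ratio of about 0.50 to 0.46 with no route effect. The intramuscular steps describe one insertion, one confirmed tip position and then withdrawal, with no repositioning stated, and the synopsis speaks of a single bolus. If the aliquots merge, the effect tends to nil. The release assumption is not in the protocol either. Neither size nor direction can be claimed.
- *That the needle wording confounds route.* It differs by period, and each route is given in both periods. Assuming the needle effect is similar for the two routes, it is a period effect that the design separates. Both descriptions are 20G and may be the same needle. This is a minor inconsistency.

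**What to change.** Before dosing, reconcile step 11 of the two lists in section 10.6 with each other and with section 10.2. There are two acceptable outcomes: state delivery pattern and duration in the same terms for both routes, or state that the pattern is part of the route being compared and word the conclusion as a comparison of the two procedures as delivered. Which pattern is used is for the clinical team.

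Separately, make the needle wording in sections 9.1.9(b), 9.1.9(d) and 10.6 step 1 agree. Again, the choice is clinical.

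The cost is a few lines in sections 9.1.9, 10.2 and 10.6 and in any worksheet the injector uses. No extra participants, visits or assays are needed. Left until after dosing, the route and pattern effects could not be separated by analysis.

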11.1. Definitions

Table 5: List of definitions for assessment of safety

Adverse Event (AE)	Any untoward medical occurrence in a patient or clinical trial participant administered a medicinal product and that does not necessarily have a causal relationship with this treatment. An AE can be any unfavourable and unintended sign (including an abnormal laboratory finding), symptom, or disease temporally associated with the use of the study medication, whether or not considered related to the study medication.
Adverse Reaction (AR)	Any untoward and unintended response in a participant to an IMP related to any dose administered to that participant. Comment: All adverse events judged by either the reporting investigator or the sponsor as having a reasonable possibility of a causal relationship to an IMP would qualify as adverse reactions. The expression ‘reasonable causal relationship’ means to convey, in general, that there is evidence or argument to suggest a causal relationship.
Safety Critical Adverse Events	Adverse events and/or laboratory abnormalities identified in the protocol as critical to safety evaluations that should be reported to the sponsor according to the reporting requirements specified in the protocol.
Serious Adverse Event (SAE)/Serious Adverse Reaction (SAR)	Any adverse event/adverse reaction that: 
 (a) results in death (b) is life-threatening (c) requires inpatient hospitalisation or prolongation of existing hospitalisation (d) results in persistent or significant disability/incapacity (e) is a congenital anomaly or birth defect 
Note: Life-threatening in the definition of a serious adverse event or serious adverse reaction refers to an event in which the participant was at risk of death at the time of the event. It does not refer to an event that hypothetically might have caused death if it were more severe.
 
Note: Medical and scientific judgement should be exercised in deciding whether an adverse event/reaction should be classified as serious in other situations. Important medical events that are not immediately life-threatening or do not result in death or hospitalisation, but may jeopardise the participant or may require intervention to prevent one of

	the other outcomes listed in the definition above should also be considered serious.
Significant Safety Issue (SSI)	
A safety issue that could adversely affect the safety of the participants or materially impact on the continued ethical acceptability or conduct of the trial.
 
e.g.: A SAE that could be associated with the trial procedures and that requires modification of the conduct of the trial.
 
A hazard to the patient population, such as lack of efficacy of an IMP used for the treatment of a life-threatening disease.
 
A major safety finding from a newly completed animal study (such as carcinogenicity).
 
A temporary halt/termination of a trial for safety reasons.
 
Recommendations of the safety monitor, where relevant for the safety of the participants, such as an increase in frequency or severity of an expected adverse reaction.
 
Single case events (e.g. toxic epidermal necrolysis, agranulocytosis, hepatic failure) that lead to an urgent safety measure.

Suspected Unexpected Serious Adverse Reaction (SUSAR)	
An adverse reaction that is both serious and unexpected.
 
A serious adverse reaction, the nature and severity of which is not consistent with the information about the medicinal product in question set out in reference safety information - summary of product characteristics relating to the trial in question.

Unexpected Adverse Reaction (UAR)	
An adverse reaction, the nature or severity of which is not consistent with the Reference Safety Information (RSI).
 
Note: The RSI should be contained in the Investigator's Brochure for an unapproved medicinal product or Product Information (or another country's equivalent of the Product Information) for an approved medicinal product.

Urgent Safety Measure (USM)	
A measure required to be taken in order to eliminate an immediate hazard to a participant's health or safety.
 
Note: This type of significant safety issue can be instigated by either the investigator or sponsor and can be implemented before seeking approval from Human Research Ethics Committees (HRECs) or institutions.

NB: To avoid confusion or misunderstanding of the difference between the terms "serious" and "severe", the following note of clarification is provided: "**Severe**" is often used to describe intensity of a specific event, which may be of relatively minor medical significance. "**Seriousness**" is the regulatory definition supplied above, and is based on patient/event outcome or action criteria usually associated with events that pose a threat to a participant's life or functioning. Seriousness (not severity) serves as a guide for defining regulatory reporting obligations.

